#### 4.1.5 Sample Size Considerations

The dose-escalation phase of the study will enroll 3-6 subjects in each cohort, based on a 3+3 dose-escalation design to assess the MTD level. A maximum of 36 subjects will enroll in the dose-escalation phase.

A maximum of 18 subjects will enroll in the expansion phase (12 additional subjects and the 6 subjects from the dose-escalation phase at the cohort of the highest dose level shown to be well tolerated or the RP2D). The expansion phase sample size of 18 subjects is not based on a formal sample size calculation. Rather, 18 subjects are deemed to be sufficient for the assessment of safety and tolerability as the primary objective and the exploration of clinical anti-tumor activity and other secondary and exploratory endpoints.

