#### 4.1.7 Dose-escalation

A standard 3+3 dose-escalation design will be used to determine MTD. The potential dose schedule is shown in section 4.1.6. In the first cohort, as a safety precaution, each new subject began treatment only after the safety analysis for DLTs and evaluation of PK data during the first cycle (28 days) was completed for the previous subject. In subsequent cohorts of the dose-escalation phase, new subjects will be entered and treated only after the previous subject has been treated with IACS-010759 for up to 7 days (e.g., has completed the induction phase) and DLT safety analysis for each subject will be performed after completion of cycle 1. PK data will be monitored for each subject and evaluated for each cohort during the study and plasma levels will be considered when making dose escalation decisions.

The following dose-escalation rules will be applied:

- If 0 out of the 3 subjects have a DLT, the next cohort may be started.
- If 1 out of the 3 subjects has a DLT, an additional 3 subjects will be enrolled in the same cohort. If none of these 3 additional subjects have a DLT after being observed for 28 days (i.e., cycle 1), the next dose escalation cohort may be started.
- If 2 or more out of 6 subjects in Cohort 1 develop a DLT, enrollment will cease immediately and the study will be halted. No MTD can be determined.
- If 2 or more out of 6 subjects in the following Cohorts (2-6) develop a DLT, enrollment into the cohort will cease, and the prior cohort's dose level will be deemed as MTD level. All subjects from the non-tolerated cohort will be de-escalated to the prior cohort's dose level.
  - If at least 2 of 3 or 2 of up to 6 patients experience a DLT at a given dose, then the MTD has been exceeded (stopping dose). Once the MTD has been exceeded, treat another 3 patients at the previous dose if there were only 3 patients treated at that dose.

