At the discretion of the sponsor, dose-escalation may be stopped before an MTD is reached. In this case, the RP2D may be chosen based on an assessment of the safety, PK, PD, biomarker, and response data evaluable up to that time. An MTD does not have to be reached to expand a dose cohort if the available data demonstrate that a lower dose level may provide antitumor activity while minimizing potential risk. Upon completion of the dose-escalation, the cohort with either the highest dose level shown to be well tolerated or the RP2D will be expanded to a total of 6 subjects (if not already expanded to 6 subjects due to either observation of a DLT or to further explore safety, PK and PD activity of IACS-010759 at that dose level).

Late onset DLTs that could not be taken into consideration prior to scheduled dose escalations will be ad-hoc evaluated on a case-by-case basis, and may lead to enrollment of additional subjects in specific cohorts or to revision of the previously determined MTD.

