#### 4.1.8 Expansion Phase

Subjects in the expansion phase will be treated at the RP2D level determined in the dose-escalation phase.

The primary objective of the expansion phase is to determine safety of IACS-010759.

Additionally, as part of the expansion phase, the effect of a high fat meal on the PK of IACS-010759 (Food Effect) will be evaluated in a total of 6 subjects (Food Effect cohort), as described in Section 7.1. After the first 6 subjects have been enrolled in the expansion cohort, the next 6 subjects will be enrolled in the Food Effect cohort.

To evaluate safety, the method of Thall, Simon and Estey [20] will be used for monitoring DLTs occurring in the first cycle. The probability of DLT is denoted by  $P_T$ . We assume  $P_T \sim$  beta (0.4, 1.6). Our stopping rule is given by the following probability statement:  $Pr(P_T > 0.20 \mid data) > 0.80$ .

That is, if at any time during the study we determine that there is more than 80% chance that the unacceptable toxicity rate is more than 20% during the expansion phase, then the enrollment will be stopped. Subjects will be monitored by a cohort size of 6 during the expansion phase according to the following stopping boundaries for DLTs, starting from the 12th

subject. The monitoring rule for DLTs, based on these assumptions and monitoring conditions is found in Table 3. For example, accrual in the expansion phase will cease if 4 or more subjects experience DLTs among the first 12 subjects. The operating characteristics are summarized in Table 4. The design software Multc Lean Desktop (version 2.1) developed by the Department of Biostatistics at M. D. Anderson Cancer Center was used to generate the toxicity stopping boundaries and the operating characteristics tables.

Table 3 Stopping boundaries for DLT monitoring

# Subjects evaluated	12	18
# Subjects with DLTs	4-12	6-18

Table 4 Operating characteristics of toxicity monitoring

True DLT Rate	Early Stopping Probability	Average Sample Size
0.10	0.0256	17.8
0.15	0.0922	17.4
0.20	0.2054	16.8
0.25	0.3512	15.9
0.30	0.5075	15.0

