#### 4.1.9.3 *Intra-Subject Dose Escalation*

Intra-subject dose escalation of IACS-010759 (in accordance with the dosing schema in Table 1 and 2) will be permitted provided:

- Subject has completed ≥2 cycles at their current dose level and has not achieved a CR or Cri
- Subject has not experienced any grade 3 or higher non-hematologic drug-related toxicity, and

Subject has not experienced DLT,

- The dose may be escalated by one dose level no more frequently than every 2 cycles.
- The escalated dose level must have been fully evaluated and shown not to exceed the MTD (0 DLT of 3 or ≤1 DLT of 6)

If an intra-subject dose escalation occurs, laboratory monitoring will be increased to weekly during the first cycle of the increase dose.

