#### 4.1.10 DLT, MTD and RP2D definitions

The MTD is defined as the highest dose studied for which the observed incidence of DLT is less than 33%. Frequencies of toxicities will be tabulated according to the NCI Common Toxicity Criteria version 4.03.

The RP2D will be determined based on the safety data and all available correlative data from the escalation phase by the Safety Monitoring Committee.

Dose-limiting toxicity (DLT) is defined as a clinically significant non-hematologic adverse event or abnormal laboratory value assessed as unrelated to disease progression, intercurrent illness, or concomitant medications and is possibly, probably or definitely related to the study drug and occurring during the first cycle (21 days) on study that meets any of the following criteria:

- All Grade 4 non-hematologic toxicities of any duration
- All grade 3 non-hematologic toxicities. Exceptions are as follow:
  - Grade 3 nausea, vomiting and diarrhea that does not require hospitalization or TPN support and can be managed with supportive care to ≤ grade 2 within 48 hours.
  - Grade 3 electrolyte abnormalities that are corrected to ≤ grade 2 within 24 hours

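### Table 4 treats all 12 subjects at the first expansion look as unselected, but 6 come from a cohort already limited to at most 1 DLT; once expansion opens, the rule stops 2.5 to 3.6 times less often than stated

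*Combined protocol and SAP*

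**What the plan says.** Section 4.1.5 sets the expansion phase at a maximum of 18: "12 additional subjects and the 6 subjects from the dose-escalation phase" at the selected dose level. Section 4.1.7 says that the chosen cohort "will be expanded to a total of 6 subjects" if it does not already have them.

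Section 4.1.8 monitors first-cycle DLTs with a beta(0.4, 1.6) prior and stops when the posterior probability that the DLT rate exceeds 0.20 is above 0.80. Monitoring is in groups of 6 from the 12th subject. Table 3 sets boundaries of 4 in 12 and 6 in 18, and the text adds that "accrual in the expansion phase will cease if 4 or more subjects experience DLTs among the first 12 subjects". Table 4 gives early stopping probabilities of 0.0256, 0.0922, 0.2054, 0.3512 and 0.5075, with average sample sizes of 17.8, 17.4, 16.8, 15.9 and 15.0, at true DLT rates of 0.10, 0.15, 0.20, 0.25 and 0.30.

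Three sections limit how many DLTs the carried-over cohort can bring:

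- Section 4.1.7: "If at least 2 of 3 or 2 of up to 6 patients experience a DLT at a given dose", the MTD has been exceeded.
- Section 4.1.10: the MTD is "the highest dose studied for which the observed incidence of DLT is less than 33" per cent. Two in 6 is 33.3%, so it fails; 1 in 6 passes.
- Section 4.1.9.3 applies the same standard (no DLT in 3, or at most 1 in 6) when it describes a dose that does not exceed the MTD.

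**The concern.** Only 12 new subjects are planned, so a look at 18 exists only if the 6 carried-over subjects are counted. The look at 12 therefore covers those 6 and the first 6 new subjects. The carried-over 6 were selected on the very outcome being monitored, and their result (0 or 1 DLT) is known before expansion opens. Table 4 gives no sign that it allows for this.

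Safety is the primary objective of the expansion phase, and Table 4 is the plan's only statement of how well the DLT rule performs. A reader deciding whether the rule is adequate would take it that a dose with a true 30% DLT rate has an even chance of being stopped with 6 new subjects still to enrol.

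The text also leaves the timing of looks unclear. Enrollment is to stop "if at any time during the study we determine that there is more than 80% chance" that the DLT rate is above 20%, yet Table 3 has no boundary before 12 or between 12 and 18.

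**Working it through.** **Inputs.** Prior, posterior cutoff, boundaries and Table 4 values: Section 4.1.8. Six carried over plus 12 new: Section 4.1.5. At most 1 DLT in the carried-over 6: Sections 4.1.7, 4.1.9.3 and 4.1.10. Subjects are taken as independent with a common true DLT rate p.

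**Step 1: Table 3.** With x DLTs in n subjects the posterior is beta(0.4 + x, 1.6 + n − x). Pr(rate > 0.20) is 0.608 at 3/12 and 0.821 at 4/12; 0.747 at 5/18 and 0.883 at 6/18. The boundaries 4/12 and 6/18 are confirmed.

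**Step 2: Table 4 as printed.** P(Bin(12, p) ≥ 4) = 0.0256, 0.0922, 0.2054, 0.3512, 0.5075, which matches to four decimals. Average size 12P + 18(1 − P) = 17.85, 17.45, 16.77, 15.89, 14.96, which matches to rounding. Adding the 18-subject boundary gives 0.0273, 0.1022, 0.2339, 0.4043, 0.5814, which does not match. So Table 4 counts only the look at 12 and takes all 12 as unselected.

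**Step 3: condition on expansion having opened.** Let X be the DLTs in the carried-over 6 and Y those in the first 6 new subjects. Stopping at 12 needs Y ≥ 4 if X = 0, or Y ≥ 3 if X = 1:

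C = [P(X=0)·P(Y≥4) + P(X=1)·P(Y≥3)] / P(X≤1)

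At p = 0.30: P(X=0) = 0.1176, P(X=1) = 0.3025, P(Y≥4) = 0.0705, P(Y≥3) = 0.2557, so

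C = (0.1176 × 0.0705 + 0.3025 × 0.2557) / 0.4202 = 0.204.

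| True rate | Stated | C | Ratio | Stated average N | Average N, 12C + 18(1 − C) |
|---|---|---|---|---|---|
| 0.10 | 0.0256 | 0.0071 | 3.6 | 17.8 | 17.96 |
| 0.15 | 0.0922 | 0.0272 | 3.4 | 17.4 | 17.84 |
| 0.20 | 0.2054 | 0.0661 | 3.1 | 16.8 | 17.60 |
| 0.25 | 0.3512 | 0.1255 | 2.8 | 15.9 | 17.25 |
| 0.30 | 0.5075 | 0.2038 | 2.5 | 15.0 | 16.78 |

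Following the 3+3 paths explicitly (0/3 then at most 1/3, or 1/3 then 0/3) gives the same C. At p = 0.30 the chance is 0.071 after 0/6 carried over and 0.256 after 1/6.

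**Step 4: sensitivity.** Suppose that subjects added to bring a 0/3 cohort up to 6 are not re-tested against the limit (0/3 then 3 unrestricted, or 1/3 then 0/3). Stopping at 12 is then 0.0098, 0.0372, 0.0893, 0.1668, 0.2659, with ratios from 2.6 down to 1.9.

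**Step 5: escalation limit and look together.** The limit rejects a dose with probability G = P(X≥2) = 0.1143, 0.2235, 0.3446, 0.4661, 0.5798. Rejection at the limit or stopping at 12 is G + (1 − G)C = 0.121, 0.245, 0.388, 0.533, 0.666.

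**Step 6: timing.** At 3 DLTs in 8 the posterior is 0.825, already above 0.80. This is reachable with 1/6 carried over and DLTs in the first 2 new subjects, but Table 3 does not act there. The look at 18 follows the last planned subject, so it cannot stop accrual.

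**The case against.** The strongest reply is that nothing in Table 4 is miscalculated. It gives the rule's properties at a fixed true rate and never claims to be conditional on the escalation result. The stopping rule itself is a posterior rule on all data at the dose, so earlier selection does not alter Table 3. The combined figures in Step 5 exceed Table 4 at every rate, so patients are better protected overall than Table 4 suggests, and the Safety Monitoring Committee can recommend termination at any time.

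All of that is correct and limits the point. It does not rescue the table, which is presented as the operating characteristics of expansion monitoring: by then the escalation limit has already been passed and half of the first 12 results are known.

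The size of the gap also depends on a strict limit of 1 in 6. Section 4.1.7 does not restate a DLT limit for subjects added to fill the cohort. It also handles "Late onset DLTs that could not be taken into consideration prior to scheduled dose escalations" case by case, and Section 4.1.10 allows prolonged myelosuppression to count as a DLT at day 42 or later, so the count at the look could exceed the count at selection. Without re-testing of added subjects, the ratios are 1.9 to 2.6; if a cohort with 2 in 6 were let through, the ratio would be about 1.4. The direction does not change.

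Finally, the 12 could be read as 12 new subjects, since Cohort 7 is listed as 12. Table 4's probability would then hold at that count, but accrual would already be complete and a look at 18 could not be reached.

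**Conclusion.** The concern holds. Table 4 is right for 12 unselected subjects but does not describe the design as written. Once expansion opens, the look at 12 stops accrual with probability 0.007 to 0.204 over true rates of 0.10 to 0.30, against a stated 0.0256 to 0.5075, and the average sample size is 17.96 to 16.78, not 17.8 to 15.0.

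This rests on the first 12 being 6 carried-over and 6 new subjects, on at most 1 DLT in the carried-over 6, and on independent subjects with a constant DLT rate. It concerns expansion-phase stopping only; it does not show that the whole design protects subjects less than Table 4 implies. It should be fixed, because it misstates the only reported performance of the rule that serves the phase's primary objective.

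**What to change.** 1. Replace Table 4 with values conditional on at most 1 DLT in the 6 carried-over subjects: stopping probability 0.007, 0.027, 0.066, 0.126, 0.204; average sample size 17.96, 17.84, 17.60, 17.25, 16.78. State the conditioning in the table title. A further column with the combined figures from Step 5 is optional but would give readers the overall picture.
2. State in Section 4.1.8 that the 12 includes the 6 carried-over subjects, and whether late-onset DLTs in those subjects count toward Table 3.
3. Note that the look at 18 is a final assessment and cannot stop accrual.
4. Reconcile the statement that the criterion applies at any time with the schedule that starts at the 12th subject. Whether to add looks before 12 or between 12 and 18 is the sponsor's choice and is not needed to correct the table.

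The cost is one recomputed table and a few sentences. No boundary, sample size or visit changes. The stated expansion-phase stopping probabilities become less favourable.

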#### 4.1.9 Dosing Adjustments, Delays and Discontinuations

IACS-010759 dose reduction/interruption/discontinuation decisions should be based on the CTCAE version 4.03 of the toxicity and according to the guidelines shown below. If toxicity is not covered in the table, doses may be reduced or held at the discretion of the investigator for the subject's safety. Additional PK, blood pH and lactate testing will be performed following a dose reduction or resumption of dosing following a dose interruption, as described in Section 4.2. IACS-010759 should be permanently discontinued in any subject that develops DLT due to lactic acid.

If a dose interruption occurs at the end of a cycle, the next cycle will be delayed and start on the first day of dosing of the next cycle. Dose interruptions which occur during a cycle will not change the study days during the cycle.

#### 4.1.9.1 IACS-010759 Dose Adjustments for Drug-Related Hematological AEs

- Subjects with acute leukemias usually present with abnormal peripheral blood counts at the
  time therapy is started and myelosuppression is an expected event during the course of
  therapy for acute leukemias. Thus, no dose adjustments or treatment interruptions for
  myelosuppression will be planned for the first 4 cycles and/or in the presence of residual
  leukemia. After that, treatment interruptions and dose adjustments may be considered
  according to the following guidelines only when there is no evidence of residual leukemia.
- Subjects with a response (e.g., no evidence of residual leukemia or cytopenias not considered to be related to leukemia) and pre-cycle counts of neutrophils >1.0 x  $10^9$ /L and platelets >50 x  $10^9$ /L who have sustained low counts of neutrophils <0.5 x  $10^9$ /L or a platelet count <20 x  $10^9$ /L for more than 2 consecutive weeks in the current cycle, may have the treatment with IACS-010759 interrupted at the discretion of the treating physician after discussing with the Principal Investigator (PI) until neutrophils recover to  $\ge 0.5 \times 10^9$ /L and platelets to  $\ge 30 \times 10^9$ /L. If prolonged myelosuppression defined as ANC <  $0.5 \times 10^9$ /L and

platelets  $< 20 \times 10^9$ /L (more than 6 weeks) with evidence of a hypocellular marrow (marrow cellularity less than 5% without evidence of leukemia) is observed, IACS-010759 will be discontinued in these subjects. Delays in the start of subsequent cycles greater than 6 weeks will be acceptable only for subjects who are deriving clinical benefit and after discussion with the Principal Investigator (PI) of potential risk/benefit ratio and complete documentation of the degree of clinical benefit and reason for continuation on this regimen.

- If there are persistent peripheral blood blasts, or the bone marrow shows >5% blasts or evidence of leukemia, treatment may be continued regardless of neutrophil and platelet count with supportive care as needed. Dose-interruptions of IACS-010759 in these subjects should be considered on an individual case and discussed with the PI and the sponsor.
- Subjects with a response (no marrow evidence of leukemia) and pre-cycle counts of neutrophils <1x10^9/L and platelets <50 x10^9/L may be continued regardless of neutrophil and platelet count with supportive care as needed. Dose-interruptions in these subjects should be considered on an individual case and discussed with the PI and the sponsor.

4.1.9.2 IACS-010759 Dose adjustments for Non-Hematologic Drug-Related AEs Dose adjustments for AEs will be performed using dose levels suggested in Table 1 and 2 in Section 4.1.6. Thus, if cohort 6 is established as the MTD, one and two dose level reductions of IACS-010759 will be the doses specified in cohort 5 and cohort 4, respectively. If the MTD is below cohort 3 further dose reduction levels of IACS-010759 will be defined before moving to the expansion phase of the study to allow for the below specified dose-reductions.

Table 5: Dose adjustments for non-hematologic drug-related AEs, clinically significant in the opinion of the investigator

Grade	Occurrence	Dose modification
1 or 2	Any time	No dose reduction.
(Persistent grade 2: Consider similar dose adjustments if persistent and not	1st and 2nd time	Hold treatment with IACS-010759.  Resume IACS-010759 at pre-interruption dose if recovery to ≤ Grade 1 or baseline occurs within 14 days. If toxicity persists for >14 days, hold therapy and resume at ONE dose level below current dose for IACS-010759 ONLY after recovery of toxicity to ≤ Grade 2.  Dose re-escalation to prior dose of IACS-010759 is not permitted.
responding to optimal management in the opinion of PI and treating physician)	3rd time	Stop treatment with IACS-010759 and discontinue subject.  (For subjects with clinical benefit/response from IACS-010759 we will consider continuation if toxicities resolve to ≤ grade 1 and with proper dose adjustments after consultation with the PI and the sponsor)
4	Any time	Stop treatment with IACS-010759 and discontinue subject.  (For subjects with clinical benefit/response from IACS-010759 we will consider continuation if toxicities resolve to ≤ grade 1 and with proper dose adjustments after consultation with the PI and the sponsor)

These general guidelines constitute guidance to the Investigator and may be supplemented by discussions with the Medical Monitor representing the Sponsor in specific cases.

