## Phase 1 Study of IACS-010759 in Subjects with relapsed or refractory AML

#### Study Synopsis and Objectives

This is an open label Phase 1 study of IACS-10579 utilizing a 3+3 dose-escalation phase followed by an expansion phase in subjects with relapsed or refractory AML and no available treatment options with known benefit.

In cohorts 1 and 2, in the first cycle, IACS-010759 will be administered on Day 1 followed by continuous dosing starting on day 8 through day 28; cycles 2 and beyond will be continuous daily dosing. Based on PK analysis and modeling of preliminary data from cohorts 1 and 2, the study design has been amended. In cohort 3 and subsequent cohorts, in the first cycle, IACS-010759 will be administered daily for up to 7 days during an initial Induction Phase (Day 1-7) followed the Maintenance Phase (Day 8-21), which will use a lower dose to maintain steady state drug levels. For cohort 3, the maintenance dose will be administered once weekly on Day 8 and Day 15 of the 21-day cycle in cycle 1; in subsequent cycles, doses will be administered on Days 1, 8 and 15 of each cycle, unless alternate schedules are recommended by the SMC. In subsequent cohorts, the induction and maintenance doses and/or the dosing interval during the maintenance phase may be further modified by the SMC based on safety, PK and PD data observed. Dosing will continue until confirmed progressive disease, initiation of alternative cancer therapy, unacceptable toxicity, or other reasons to discontinue treatment prematurely at the dose levels given below:

Original Dose Escalation Regimen, Cohorts 1 and 2:

PHASE	COHORT	NO OF SUBJECTS	IACS-010759 DOSE LEVEL (DAILY EXCEPT CYCLE 1, DAY 2-7) *
Dose-	Cohort 1	3-6	0.5 mg
escalation	Cohort 2	3-6	1 mg

\*Intermediate doses of IACS-010759, not to exceed 8 mg, not listed above may also be pursued with SMC approval depending on the safety, PK and PD data observed.

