Limited PK data from subjects in cohorts 1 and 2 showed unexpected levels of accumulation of IACS-010759 throughout the dosing period, consistent with a model in which the clearance of IACS-010759 decreases exponentially with time, leading to an increasingly long terminal  $T_{1/2}$  and accumulation upon multiple dosing. A mathematical model and simulation has been developed based on data from the subjects treated with IACS-010759 to date that predicts the observed human PK. Based on this model, a modified dosing regimen is being implemented for the dose escalation phase with cohorts 3-6 and for the dose expansion phase with cohort 7, consisting of an induction phase in which IACS-010759 is administered daily for up to 7 days, followed by a maintenance phase in which a lower dose is administered weekly to maintain steady state plasma levels (or as otherwise specified by the SMC based on safety, PK and PD data observed).

Page 17 of 59

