#### 4.1.9.4 Other Allowable Modifications of Dose Schedules

Other modifications of dose schedules than the above will be allowed within the following guidelines:

- Further dose reductions can be made to keep clinically significant toxicities grade < 2.
   
Dose adjustments by more than 1 dose level at a time (e.g., from cohort 6 dose to cohort 4 dose) can be considered when judged in the best interest of the subject (e.g. severe myelosuppression, lactic acidosis) when the toxicity has resolved. The reason for this reduction will be discussed with the PI or Co-PI and documented in the medical record.
- Treatment interruptions and dose modifications other than the ones mentioned above can be considered after discussion with the PI, sponsor and proper documentation of the rationale.

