### 6 Study Drug

### 6.1 Study Drug Administration

Cohorts 1 and 2: For each cycle 1, a single oral dose of IACS-010759 will be administered on day 1. The next dose of IAC-010759 will be administered on day 8, and daily continuously for the duration of the study with no interruptions unless there are adverse events as described in Section 4.1.9. IACS-010759 doses will be separated by intervals of approximately 24 hours (+/- 3 hours).

Cohorts 3-6 and Dose Expansion: Based on the observed accumulation of IACS-010759 throughout the dosing period in cohorts 1 and 2, a modified dosing regimen is being implemented, consisting of an induction phase in which IACS-010759 is administered daily for up to 7 days, followed by a maintenance phase in which a lower dose is administered weekly (or as otherwise specified by the SMC based on safety, PK and PD data observed) to maintain steady state plasma levels. Dosing will proceed on this schedule for the duration of the study with no interruptions unless there are adverse events as described in Section 4.1.9.

IACS-010759 will be administered without food, at least 1 hour before and at least 2 hours after eating. Each dose of IACS-010759 should be administered with 8 ounces of water. If a dose is missed, the next dose will not be increased to account for missing a dose. The subject will take the next regular dose at the scheduled time. Following cycle 1 (28-day cycle for cohorts 1 and 2, 21 day cycle for subsequent cohorts), subjects will receive one cycle of therapy every 21 days (+/- 4 days).

In cohorts 1 and 2, treatment was administered as an inpatient for 24 hours on day 1 and then starting on day 8 for the next 7 days for all enrolled subjects. In cohorts 3 and 4, treatment will be administered as an inpatient for 24 hours on Day 7 of Cycle 1 for all enrolled subjects. In subsequent cohorts, treatment will be administered as an inpatient for 24 hours on Day 5 of Cycle 1 for all enrolled subjects. IACS-010759 will be self-administered and subjects instructed not to dose on days when PK/PD samples are collected until advised by the research staff. Self-administration can occur on days without PK/PD and subjects will record administration in a provided diary.

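### Adverse-event dose reductions follow cohort number, but weekly dose does not: the step from cohort 3 to cohort 2 raises the dose, from 0.5 mg to 1, 3 or 7 mg a week depending on the schedule applied

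*Combined protocol and SAP*

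**What the plan says.** Section 4.1.9.2 ties reductions for non-hematologic drug-related events to both dosing tables: "Dose adjustments for AEs will be performed using dose levels suggested in Table 1 and 2". Its one worked example starts at cohort 6 and names cohorts 5 and 4 as one and two levels down. It makes one exception: "If the MTD is below cohort 3 further dose reduction levels of IACS-010759 will be defined before moving to the expansion phase".

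Table 5 in the same section sets the trigger. At the first and second occurrence treatment is held. Recovery within 14 days returns the subject to the same dose; otherwise, "If toxicity persists for >14 days, hold therapy and resume at ONE dose level below current dose". It adds that "Dose re-escalation to prior dose of IACS-010759 is not permitted". A third occurrence, or grade 4, normally ends treatment.

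Section 4.1.9.4 also counts by cohort number: "Dose adjustments by more than 1 dose level at a time (e.g., from cohort 6 dose to cohort 4 dose) can be considered".

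On schedule, the synopsis table for cohorts 1 and 2 is headed "IACS-010759 DOSE LEVEL (DAILY EXCEPT CYCLE 1, DAY 2-7", so those cohorts are dosed daily. Cohorts 3 to 6 have a daily induction and then maintenance once a week (cohort 3) or three times a week (cohorts 4 to 6). For cohorts 3 to 6 and the expansion, Section 6.1 says "Dosing will proceed on this schedule for the duration of the study".

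**The concern.** A reduction ladder has to go down. This one joins two regimen families, daily dosing in Table 1 and intermittent maintenance in Table 2, and numbers them as one sequence. Cohort 3 is the highest of the first three cohorts by induction dose, but it has the lowest weekly dose of all six once induction is over. A subject being reduced is normally past induction, so the post-induction dose is the one that matters.

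At stake is a subject with drug-related toxicity lasting more than 14 days who, by the stated rule, resumes on more drug than before. On the daily reading the subject would also move to the schedule that Section 3.1 says was replaced because cohorts 1 and 2 showed "unexpected levels of accumulation of IACS-010759 throughout the dosing period".

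**Working it through.** **Inputs.** Doses and frequencies are from Tables 1 and 2 in Section 4.1.6. Weekly dose = mg per dose × doses per week, after induction (cohorts 3 to 6) or lead-in (cohorts 1 and 2).

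**Check against the plan's own figure.** The only weekly total the protocol states is 3 mg for cohort 4. 1.0 × 3 = 3 mg, which agrees.

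| Cohort | Calculation | mg/week |
|---|---|---|
| 1 | 0.5 × 7 | 3.5 |
| 2 | 1 × 7 | 7 |
| 3 | 0.5 × 1 | 0.5 |
| 4 | 1.0 × 3 | 3 |
| 5 | 1.5 × 3 | 4.5 |
| 6 | 2 × 3 | 6 |

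**Two reductions by cohort number, each cohort on its own schedule (mg/week).**

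| Start | Start dose | First reduction | Second reduction |
|---|---|---|---|
| Cohort 6 | 6 | 4.5 | 3 |
| Cohort 5 | 4.5 | 3 | 0.5 |
| Cohort 4 | 3 | 0.5 | 7 |
| Cohort 3 | 0.5 | 7 | 3.5 |

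The first two rows fall throughout. The last two do not.

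**The step from cohort 3 to cohort 2 under each schedule reading.** The protocol does not say which schedule a reduced subject follows.

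- Daily, as cohort 2 was dosed: 1 × 7 = 7 mg/week. 7/0.5 = 14 times the previous step; 7/3 = 2.3 times the cohort 4 dose.
- Three times weekly: 1 × 3 = 3 mg/week. 3/0.5 = 6 times the previous step; equal to the cohort 4 dose.
- Once weekly: 1 × 1 = 1 mg/week. 1/0.5 = 2 times the previous step; one third of the cohort 4 dose.

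Per 21-day cycle, cohort 4 gives 9 mg, cohort 3 gives 1.5 mg, and the cohort 2 step gives 21, 9 or 3 mg.

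**One further reading.** A cohort 4 subject might keep three-times-weekly dosing throughout and take only the milligram amount from each lower cohort. The path is then 1 × 3 = 3, 0.5 × 3 = 1.5, 1 × 3 = 3 mg/week. The second reduction doubles the dose and returns it to the level the subject was first reduced from, which Table 5 forbids.

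**Multi-level drops.** Under Section 4.1.9.4, two levels down from cohort 4 is cohort 2 directly: from 3 mg/week to 7 (daily), 3 (three times weekly) or 1 (once weekly).

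**Reach of the exception.** It is triggered by an MTD below cohort 3. An MTD at cohort 3 uses cohorts 2 and 1 as its lower levels; an MTD at cohort 4 uses cohorts 3 and 2. Both contain the faulty step and neither triggers the exception.

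**The case against.** The best defence is that the step is inferred. The only example runs from cohort 6 to cohort 4; nowhere is a cohort 3 subject told to go to cohort 2. Table 5 speaks of a level below the current dose, and a larger weekly dose is not below it, so the text could be said to leave the lower level undefined rather than to prescribe an increase. This does not clear the plan. The rule names both tables, the count is by cohort number in two sections, and the exception begins only under cohort 3, which makes sense only if cohorts 2 and 1 are regarded as usable reductions for cohort 3. No other level below cohort 3 is given.

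The second objection stands in part. A reader might infer that the plan mandates a 14-fold increase to 7 mg/week. The documents do not support that as fact. The synopsis puts expansion subjects on induction plus maintenance, and Section 6.1 keeps cohorts 3 to 6 and the expansion on their schedule. With an intermittent schedule, the second reduction from cohort 4 gives 1 or 3 mg/week, no more than the starting dose. What remains on every reading is that this reduction raises the dose from the step before it.

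Third, there are safeguards. Table 5 is described as guidance, Section 4.1.9.4 allows other modifications after discussion, the SMC can approve intermediate doses and schedules, PK is sampled around reductions, and a DLT due to lactic acid leads to permanent discontinuation (Section 4.1.9). These lower the risk, but they depend on someone noticing that the listed lower level is higher. They do not correct the default.

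**Conclusion.** The reduction ladder in Section 4.1.9.2 is wrong as written below cohort 4, and Section 4.1.9.4 repeats the counting rule. The step from cohort 3 to cohort 2 raises the weekly dose from 0.5 mg to 7, 3 or 1 mg by schedule. This rests on the reading that levels run by cohort number through both tables, and on comparing subjects past induction. Within the induction week cohort 3 gives 2 × 7 = 14 mg against 7 mg for cohort 2 daily, so there the step would be a decrease.

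The scope is narrow. It covers subjects on the cohort 3 or 4 regimen, including cohort 5 subjects whom Section 4.1.7 would de-escalate to cohort 4, and the 12 new expansion subjects if cohort 3 or 4 becomes the MTD or RP2D. From cohort 4 the faulty step needs either a second prolonged toxicity or a two-level drop.

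Three stronger inferences are not supported:

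- How fast plasma levels would overtake those on cohort 4. Section 3.1 reports clearance that falls with time, and the half-lives given are from animals.
- How many subjects would be affected. The documents give no rate of repeated prolonged toxicity.
- That Section 4.1.7 is also at fault for labelling cohort 4 the MTD if cohort 5 fails. Cohort 4 must pass its own 3+3, the SMC sets the RP2D, and intermediate regimens are already allowed.

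**What to change.** In Section 4.1.9.2, for subjects on induction plus maintenance:

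- Order reduction levels by weekly maintenance dose (6, 4.5, 3, 0.5 mg) and state that the cohort 1 and 2 daily regimens are not reduction levels.
- Extend the exception to an MTD or RP2D at cohort 3 or 4, and to escalation subjects on those regimens. The SMC then sets levels below 0.5 mg weekly from PK, or the subject discontinues. Two reductions need one such level from a cohort 4 start and two from a cohort 3 start. The 0.1 mg capsule in Section 6.2 makes these feasible.
- State in Section 4.1.9.4 that multi-level drops use the same ladder.

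The cost is a wording amendment plus the SMC's choice of the lower levels. It needs no extra subjects and no new capsule strength.
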